1.0 BACKGROUND

1.1 Overview

Acute lymphoblastic leukemia (ALL) remains one of the most common hematologic diseases for which allogeneic hematopoietic cell transplantation (HCT) is currently used.¹ Despite improved outcomes of HCT over time for ALL, relapse remains a considerable problem and the leading cause of treatment failure.² There is mounting evidence to support that for patients in hematological complete remission (< 5% leukemia in the bone marrow), the presence of minute amounts of leukemia (known as minimal residual disease (MRD)), identified immediately prior to HCT is associated with higher rates of ALL relapse following HCT.³⁻¹² This trial will determine if blinatumomab used as a bridge to HCT can reduce rates of subsequent relapse and improve post-HCT survival. If successful, this strategy could become standard of care for patients going to HCT for B-ALL with residual disease.

1.2 Rationale for Studying Blinatumomab in Relapse B-ALL

Survival for relapse of B-ALL is suboptimal with outcomes ranging 30-50%.¹³ Additionally, there is mounting evidence to support that for patients in hematological remission, the presence of minimal residual disease (MRD), identified immediately prior to allogeneic hematopoietic cell transplantation (HCT), is associated with higher rates of relapse following HCT. Patients who have MRD identified prior to HCT, have relapse rates of 50-60% compared to 10-20% for patients who are MRD negative.⁶ In the Children's Oncology Group (COG) study ASCT0431 reporting HCT outcomes in 144 pediatric patients with relapse ALL, those who achieved MRD negativity pre-HCT identified by flow cytometry (FC) reported significantly less relapse at 1-year (20% versus 60%, p=0.4).¹² Even more impressive was the predictability of relapse using high throughput sequencing (HTS) for MRD detection which was superior to FC. Patients on the ASCT0431 study who achieved HTS-MRD negativity pre-HCT had no relapses compared to those who were HTS-MRD positive (0% versus 16%, p=0.02) and significantly greater overall survival (96% versus 77%, p=0.003).¹⁴ Additionally, post-HCT HTS-MRD detection was better at predicting relapse than FC-MRD (p<0.0001), especially early after HCT (day 30 FC-MRD positive relapse rate, 35%; HTS-MRD positive relapse rate, 67%; p=0.004). Thus, introducing therapies for patients who are MRD positive prior to HCT to eliminate MRD and potentially improve post-HCT survival, is a promising approach and the primary focus of this study.

Blinatumomab is a promising novel agent for the treatment of B-lineage lymphoid malignancies.¹⁵⁻¹⁹ Blinatumomab is a bispecific single-chain antibody that targets the CD19 antigen and redirects CD3+ T-cells for selective lysis of tumor cells. In a Phase 2 trial of adult B-ALL, patients with MRD persistence or relapse after Induction and Consolidation therapy received Blinatumomab as a 4-week continuous intravenous infusion at a dose of 15 µg/m²/24 hours.¹⁹ Of 21 treated patients, 16 became MRD negative as assessed by quantitative polymerase chain reaction (QT-PCR) for either rearrangements of immunoglobulin or T-cell receptor genes, or specific genetic aberrations. Among the 16 responders, 12 had been molecularly refractory to previous chemotherapy. Probability for relapse-free survival was 78% at a median follow-up of 405 days. Blinatumomab was similarly effective and well tolerated in an anecdotal report of a small series of pediatric cases.¹⁶

Blinatumomab has been evaluated in children with relapsed/refractory ALL in Phase 1/2 study conducted by the Children's Oncology Group (COG) (MT103-205/AALL1121) and the I-BFM

European childhood leukemia cooperative group with extremely promising results. Forty-nine patients were treated in the Phase 1 portion and 44 patients in the Phase 2.²⁰ Four patients had dose-limiting toxicities in Cycle 1 (Phase 1). Three experienced Grade 4 cytokine-release syndrome (one attributed to Grade 5 cardiac failure); one had fatal respiratory failure. The maximum-tolerated dosage was 15 $\mu\text{g}/\text{m}^2/\text{d}$. Blinatumomab pharmacokinetics was linear across dosage levels and consistent among age groups. On the basis of the Phase 1 data, the recommended Blinatumomab dosage for children with relapsed/refractory ALL was 5 $\mu\text{g}/\text{m}^2/\text{d}$ for the first 7 days, followed by 15 $\mu\text{g}/\text{m}^2/\text{d}$ thereafter. Among the 70 patients who received the recommended dosage, 27 (39%; 95% CI, 27% to 51%) achieved complete remission within the first two cycles, 14 (52%) of whom achieved complete MRD response. The most frequent Grade ≥ 3 adverse events were anemia (36%), thrombocytopenia (21%), and hypokalemia (17%). Three patients (4%) and 1 patient (1%) had cytokine-release syndrome of Grade 3 and 4, respectively. Two patients (3%) interrupted treatment after Grade 2 seizures. This trial was the first such trial in pediatrics and demonstrated anti-leukemic activity of single-agent Blinatumomab with complete MRD response in children with relapsed/refractory B-ALL.

In December 2014, the COG opened a Phase 3 study group-wide (>100 institutions) investigating blinatumomab in combination with chemotherapy for children, adolescents and young adults with 1st relapse B-ALL (AALL1331; NCT02101853). The dose used in this study for patients who are in remission is 15 $\mu\text{g}/\text{m}^2/\text{d}$ (maximum dose of 28 mcg/d). This study continues to accrue.

The level of single agent activity seen with blinatumomab has not been seen in recent Phase 1 ALL studies outside the use of tyrosine kinase inhibitors (TKI) in patients with Philadelphia chromosome positive (Ph+) ALL.

Neurological adverse events have been described with blinatumomab and will be closely monitored on this study. One potential concern regards the safety of combining blinatumomab with IT chemotherapy which is given prior to starting blinatumomab on this study. However, in the previous Phase 1/2 pediatric study cited above, IT methotrexate or IT triples were included prior to Cycle 1, at Day 15 of Cycle 1 and at Day 29 of each cycle with no unusual or increased CNS side effects reported.²⁰

Cytokine release syndrome (CRS) has also been described with blinatumomab. This has been more prevalent in patients with a higher leukemia burden, however, can occur in any patient treated with blinatumomab. Pre-medication with dexamethasone will be mandated in the protocol, and at the suggestion of the development of CRS, even after the premedication doses, additional dexamethasone administration is suggested. There is a published case report suggesting that for cases of life-threatening cytokine release syndrome for which dexamethasone and supportive care measures are not adequate, consideration may be given to the administration of tocilizumab, the anti-IL-6 monoclonal antibody.²¹

On July 11, 2017, the US FDA approved blinatumomab for treatment of relapsed or refractory B-cell ALL in adults and children and in March 2018, the US FDA granted accelerated approval to blinatumomab to treat adults and children with B-cell ALL who are in remission but still have MRD. The FDA approved dose of blinatumomab in children and adults who have < 5% leukemia blasts in the bone marrow is 15 $\mu\text{g}/\text{m}^2/\text{d}$ (patients < 45kg; not to exceed 28 $\mu\text{g}/\text{d}$) and 28 $\mu\text{g}/\text{d}$ (patients ≥ 45 kg) as a continuous infusion for 28 days.

2.0 HYPOTHESIS AND OBJECTIVES

2.1 Hypothesis

Blinatumomab will successfully reduce the leukemia disease burden (as measured by HTS) for children, adolescents and young adults with relapse or persistent MRD B-ALL when given prior to HCT, resulting in improved post-HCT outcomes.

2.2 Primary Objectives

To determine the efficacy of blinatumomab given immediately prior to HCT as “bridging therapy” to eliminate MRD using flow cytometry in children, adolescents and young adults with relapse or persistent MRD B-ALL.

2.3 Secondary Objectives

To compare the results of Flow Cytometry-based versus molecular High-Throughput Deep Sequencing-based minimal residual disease (MRD) testing following blinatumomab prior to HCT in children, adolescents and young adults with relapse or persistent MRD B-ALL and how these MRD correlate with post-HCT outcomes.

3.0 STUDY DESIGN

3.1 General Description

This Phase 2 study will determine the effectiveness of delivering 1 to 2 cycles of blinatumomab (Days 1-28) as bridging therapy in children, adolescent and young adults with B-ALL and MRD. Eligible subjects, ages \leq 25 years with the diagnosis of B-ALL in hematologic complete remission ($< 5\%$ leukemia in the bone marrow) and evidence of MRD ($\geq 0.01\%$), will receive 1 or 2, 28-day cycles of blinatumomab prior to proceeding to HCT. Centralized MRD assessment will be performed after completion of the 28-days of blinatumomab using both Flow Cytometry (University of Washington, [name] or local lab if applicable) and High-Throughput Deep Sequencing (HTS) MRD technologies (Adaptive Technologies, Seattle, WA). Subjects who achieve Flow Cytometry negative MRD ($< 0.01\%$) after a single cycle of blinatumomab can proceed directly to HCT whereas subjects who remain MRD positive by Flow Cytometry may remain on study to receive a 2nd cycle of blinatumomab. Additionally, subjects who achieved MRD negativity after Cycle 1 but are unable to proceed to HCT based on the timing/scheduling of the donor collection, a 2nd cycle of blinatumomab may be given. This additional cycle of blinatumomab for subjects awaiting donor collection, may be 28 days but can be less if the HCT is ready to proceed (e.g. 14-day blinatumomab infusion). Subjects who remain MRD positive by Flow Cytometry after a 2nd cycle of blinatumomab will be considered a treatment failure and come off study. For patients who achieve MRD negativity via Flow Cytometry and proceed to HCT, centralized HTS MRD assessment (Adaptive Technologies, Seattle, WA) will be used to determine which conditioning regimen will be given as patients who are MRD negative by Flow Cytometry but have MRD identified by HTS will receive standard myeloablative conditioning whereas patients achieving MRD negativity with both Flow Cytometry and HTS (MRD undetectable), will receive non-myeloablative conditioning. This is part one of a two-part study. The current study is measuring the timing of blinatumomab in relation to HCT. In the second part of the study, the subjects move on to receive a transplant if they achieve an MRD negative status.

3.2 Number of Subjects

This Phase 2 study will enroll up to 35 subjects with the goal of achieving 25 evaluable subjects who become MRD negative based on Flow Cytometry after completing 1 to 2 cycles of blinatumomab and successfully proceed to HCT.

3.3 Primary Completion

The study will reach primary completion for enrollment 30 to 36 months from the time the study opens to accrual.

3.4 Study Completion

The study will reach final study completion 42-48 months from the time the study opens to accrual.

4.0 PATIENT SELECTION

Study entry is open to patients regardless of gender or ethnic background. While there will be every effort to seek out and include females and minority patients, the patient population is expected to be no different than that of other acute leukemia studies at the Medical College of Wisconsin.

4.1 Eligibility Criteria

Patients must have baseline evaluations performed prior to the start of blinatumomab and must meet all inclusion and exclusion criteria. In addition, the patient must be thoroughly informed about all study aspects, including the study visit schedule and required evaluations and all regulatory requirements for informed consent. The written informed consent must be obtained from the patient prior to enrollment. The following criteria apply to all patients enrolled onto the study unless otherwise specified.

4.2 Inclusion Criteria

4.2.1 Diagnosis of B-ALL in hematologic complete remission (defined as an M1 marrow, < 5% blasts) with MRD in the bone marrow ($\geq 0.01\%$) by multi-parameter flow cytometry and that meets one of the following:

- Patients in first relapse or greater;

OR

- Patients with very-high risk biology ALL that is proceeding to HCT in first remission (e.g. Induction failure, Severe-hypodiploidy, Ph-like ALL);

OR

- Patients who have persistent MRD after Consolidation therapy (End of Consolidation (EOC) MRD positive $\geq 0.01\%$);

AND with the intent of going on to an allogeneic hematopoietic cell transplantation (HCT) independent of this study

- 4.2.2 Patients must have an available donor and have intention of proceeding directly to HCT after completion of 1 to 2 cycles of Bridging therapy with blinatumomab.
- 4.2.3 Age \leq 25 years at time of study enrollment
- 4.2.4 Karnofsky Performance Status \geq 50% for patients 16 years and older and Lansky Play Score \geq 50 for patients under 16 years of age (see Appendix 1)
- 4.2.5 Have acceptable organ function as defined within 7 days of study registration:

Renal: creatinine clearance \geq 60 mL/min/1.73m² **or** serum creatinine based on age/gender as follows:

Age	Maximum Serum Creatinine (mg/dl)	
	Male	Female
1 month to < 6 months	0.4	0.4
6 months to < 1 year	0.5	0.5
1 year to < 2 years	0.6	0.6
2 years to < 6 years	0.8	0.8
6 years to < 10 years	1.0	1.0
10 years to < 13 years	1.2	1.2
13 years to < 16 years	1.5	1.4
\geq 16 years	1.7	1.4

Hepatic: ALT < 5 x upper limit of normal (ULN) and total bilirubin \leq 1.5 x upper limit of normal (ULN) for age

Cardiac: left ventricular ejection fraction \geq 40% by ECHO/MUGA

- 4.2.6 At least 7 days must have elapsed from prior chemotherapy.
- 4.2.7 Patients who have experienced their relapse after HCT are eligible, provided they have no evidence of acute or chronic Graft-versus-Host Disease (GVHD) and are off all transplant immune suppression therapy for at least 7-days (e.g. steroids, cyclosporine, tacrolimus). Steroid therapy for non-GVHD and/or non-leukemia therapy is acceptable.
- 4.2.8 Biologic (anti-neoplastic agent): At least 7 days after the last dose of a biologic agent. For agents that have known adverse events occurring beyond 7 days after administration, this period must be extended beyond the time during which adverse events are known to occur. The duration of this interval must be discussed with the study chair. Patients with Philadelphia-chromosome positive or Philadelphia-chromosome like (PH-Like) BALL are an exception to this eligibility criteria as concomitant TKI therapy is allowed on study (e.g. imatinib, dasatinib, nilotinib).

- 4.2.9 Monoclonal antibodies: At least 3 half-lives of the antibody must have elapsed after the last dose of monoclonal antibody (i.e. Inotuzumab = 12 days).
- 4.2.10 Immunotherapy: At least 42 days after the completion of any type of immunotherapy (e.g. tumor vaccines or CAR T-cell therapy) **except monoclonal antibodies**.
- 4.2.11 XRT: Cranio or craniospinal XRT is prohibited during protocol therapy. ≥ 90 days must have elapsed if prior TBI, cranio or craniospinal XRT
- 4.2.12 Sexually active females of child-bearing potential must agree to use adequate contraception (diaphragm, birth control pills, injections, intrauterine device [IUD], surgical sterilization, subcutaneous implants, or abstinence, etc.) for the duration of treatment and for 2 months after the last dose of chemotherapy. Sexually active men must agree to use barrier contraceptive for the duration of treatment and for 2 months after the last dose of chemotherapy.
- 4.2.13 Voluntary written consent before performance of any study-related procedure not part of normal medical care, with the understanding that consent may be withdrawn by the subject at any time without prejudice to future medical care.

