Version No.	Revision Date	Summary of Changes	Consent Revised Yes/No
1.4	06/14/2021	PI Requested changes as follows: 
 Removal of [name] from the protocol Addition of TKI use for Ph+ and Ph-like B- ALL to eligibility criteria Addition of CMV/EBV serologies to screening procedures 	Yes 
 Added viral serologies to screening procedures
1.3	03/01/2021	PI Requested changes as follows: 
 Physician visits changed to weekly in study calendar and Section 5.2.1 Added additional cycle of blinatumomab for MRD negative subjects that have issues with timing of donor collection on pages Added note that MRD by HTS does not need to be completed within the 14 day window in section 5.1.3 Follow up visits to revised as “weekly in Section 5.4.1 Off study criteria added in Section 5.6.6 Added option of using local lab for MRD by flow since this can be done at CW lab Various administrative changes 	Yes 
 Physician visits revised to weekly Administrative edits
1.2	01/27/2021	Added NGS testing that identifies BOTH B and T cell proteins. Updated under study calendar, section 5.1.3, section 5.3.1 and section 6.2.	No
1.1	10/26/2020	FDA Requested changes as follows: 
 Section 6 revised to add minimal organ functions Section 6.3.5 revised to add a statement referring to Appendix 2 which refers to the current USPI for volume calculations Risk of Serious Adverse Reactions in Pediatric Patients due to Benzyl Alcohol Preservative was added to Section 6.3.7 Blinatumomab AE List in Section 8.3 was revised as per the risks provided by Amgen Appendix 2 revised to add “do not shake” to #3 discussing adding IV solution stabilizer Appendix 2 revised to add a statement for Patients Weighing Under 22 kg Appendix 2 revised to remove all volume calculation tables and refer to the current USPI for preparation 
Local Changes as follows: Removal of [name] from list of Sub-Investigators
	Yes 
 Added “Do not drive, operate heavy machinery, etc. under risks section Added CRS, Neurological problems, and Infections as separate bullets to “Health Risks or Problems” Blina AE list was revised Added drug monograph for dexamethasone

ABSTRACT

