4.3 Exclusion Criteria

- 4.3.1 History of CNS3 disease and/or active central nervous system (CNS) disease (\geq CNS2)
- 4.3.2 Receiving concomitant chemotherapy (with the exception of a tyrosine kinase inhibitor (e.g. imatinib, dasatinib, nilotinib) for Philadelphia-chromosome positive or Philadelphia-chromosome Like (Ph-Like) BALL), radiation therapy; immunotherapy or other anti-cancer therapy other than is specified in the protocol.
- 4.3.3 Systemic fungal, bacterial, viral, or other infection not controlled (defined as exhibiting ongoing signs/symptoms related to the infection and without improvement, despite appropriate antibiotics or other treatment)
- 4.3.4 Pregnant or lactating. The agents used in this study are known to be teratogenic to a fetus and there is no information on the excretion of agents into breast milk. All females of childbearing potential must have a blood test or urine study within 7-days prior to the start of blinatumomab to rule out pregnancy.
- 4.3.5 Known allergy to blinatumomab
- 4.3.6 Participating in a concomitant Phase 1 or 2 study

5.0 REGISTRATION PROCEDURES (STUDY ENTRY, STUDY PROCEDURES, END OF TREATMENT AND WITHDRAWL PROCEDURES)

Registration will occur after eligibility is confirmed and the patient/parent has signed the subject consent, but before any treatment has been administered. Questions regarding eligibility should be directed to the Principal Investigator: [name] ([contact]; email

[contact])

The eligibility checklist will be completed at the time of study enrollment.

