10.5 Analyses Plans

The primary objective is to determine the efficacy of giving blinatumomab immediately prior to HCT as “bridging therapy” to eliminate MRD (as measured by flow cytometry) in children, adolescents and young adults with relapse, refractory or persistent MRD B-ALL.

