10.7.2 Primary Endpoint

The proportion of subjects who are FC-MRD negative (< 0.01%) will be summarized with 95% CI.

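### Concomitant TKI is allowed for Ph+ and Ph-like subjects, but the primary analysis pools them with blinatumomab-only subjects, so the pooled response rate cannot be credited wholly to blinatumomab

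*Combined protocol and SAP*

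**What the plan says.** **Eligibility.** The version 1.4 entry in the revision history records "Addition of TKI use for Ph+ and Ph-like B- ALL to eligibility criteria". In the current text, Section 4.2.8 exempts Ph+ and Ph-like disease from the washout for biologic agents: "concomitant TKI therapy is allowed on study (e.g. imatinib, dasatinib, nilotinib". Section 4.3.2 bars other concomitant anti-cancer treatment "with the exception of a tyrosine kinase inhibitor (e.g. imatinib, dasatinib, nilotinib) for Philadelphia-chromosome positive or Philadelphia-chromosome Like (Ph-Like) BALL". Ph-like ALL is a named route into the study under Section 4.2.1: "Patients with very-high risk biology ALL that is proceeding to HCT in first remission (e.g. Induction failure, Severe-hypodiploidy, Ph-like ALL". No section requires a TKI to have been started, or held stable, before entry.

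**Objective.** Section 2.2 reads "To determine the efficacy of blinatumomab given immediately prior to HCT", and Section 10.5 repeats it: "The primary objective is to determine the efficacy of giving blinatumomab immediately prior to HCT". Neither mentions a TKI.

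**Analysis.** Section 10.7.2 reads "The proportion of subjects who are FC-MRD negative (< 0.01%) will be summarized with 95% CI". The primary efficacy group in Section 10.6 is everyone with at least one completed course and an MRD assessment. Section 10.4 tests the rate against a null of 0.40. The only planned comparison (Section 10.7.4) sets HTS-negative against HTS-positive subjects, by demographics and number of cycles. TKI use does not appear in Section 10.

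**Data.** Concomitant medications are reviewed weekly during treatment and follow-up (Sections 5.2.1 and 5.4.1), and baseline medications are recorded (Section 5.1.3).

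**The concern.** With no control arm, the inference rests on everyone receiving the same treatment of interest and on 40% being a fair benchmark for it. A TKI is the one additional anti-leukemic treatment that the protocol lets in, and the protocol treats it as active in at least one setting. Section 1.2 says that blinatumomab's level of single-agent activity had not been seen in recent Phase 1 ALL studies "outside the use of tyrosine kinase inhibitors (TKI) in patients with Philadelphia chromosome positive (Ph+) ALL". A subject who clears MRD on both drugs counts as a full success for blinatumomab.

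Two results are exposed: the estimate in Section 10.7.2, which becomes a mixture of two treatments, and the count rule in Section 10.4, where two or three responses out of 25 can decide the outcome. A reader of the final report could not tell how far either depends on TKI users.

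**Working it through.** **Inputs from the documents (Section 10.4).** Null rate 0.40; 25 evaluable subjects; fewer than 15 responses misses a 60% threshold; success is also defined as at least 67%, which needs 17 of 25 because 0.67 × 25 = 16.75. Stated type I error 0.0333; stated power 0.8071 at 0.67.

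**Inputs assumed.** The number of TKI users, k, is taken as 2, 3 or 4 of 25. Their response rate, q, is taken as 40% to 100%. The documents give neither.

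**Step 1: the plan's own figures.** Enumerating the two-stage rule as printed (12 then 13 subjects; R ≤ 4, R ≥ 10, then at least 15 of 25) gives type I error 0.0350 and power 0.8303. With R ≤ 5 at stage 1 the results are 0.0333 and 0.8152. So the stated error rate matches R ≤ 5, not the printed R ≤ 4, and neither version gives the stated power. That is a separate matter. A plain tail, P(Bin(25, 0.40) ≥ 15), gives 0.0344. It is used below because the printed stage 1 limits lead to re-evaluation or comment, not to a mandatory stop. The printed two-stage rule gives nearly the same results (0.035 with no users; 0.082, 0.120 and 0.175 for 2, 3 and 4 users who all respond).

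**Step 2: effect on the estimate.** With the other subjects at 0.40, the expected pooled rate is 0.40 + (k/25)(q − 0.40).
- k = 2: 0.416 at q = 0.60, 0.448 at q = 1.00
- k = 3: 0.424 to 0.472
- k = 4: 0.432 to 0.496

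**Step 3: effect on the count rule.** Let X ~ Bin(25 − k, 0.40) and Y ~ Bin(k, q), independent. The quantity is P(X + Y ≥ r).

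| k | r | q = 0.40 | q = 0.60 | q = 0.80 | q = 1.00 |
|---|---|---|---|---|---|
| 0 | 15 | 0.0344 | – | – | – |
| 2 | 15 | 0.0344 | 0.0481 | 0.0637 | 0.0813 |
| 3 | 15 | 0.0344 | 0.0565 | 0.0851 | 0.1207 |
| 4 | 15 | 0.0344 | 0.0661 | 0.1119 | 0.1744 |
| 0 | 17 | 0.0043 | – | – | – |
| 2 | 17 | 0.0043 | 0.0067 | 0.0095 | 0.0128 |
| 3 | 17 | 0.0043 | 0.0083 | 0.0139 | 0.0215 |
| 4 | 17 | 0.0043 | 0.0102 | 0.0200 | 0.0352 |

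If every TKI user responds, the remaining subjects reach the 15-response line with 13 of 23, 12 of 22 or 11 of 21.

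**Step 4: can the two analyses be compared by whether each CI excludes 40%?** Exact (Clopper-Pearson) limits fit the plan: 20 of 25 gives 0.593–0.932, matching the printed (0.59, 0.93). But 16 of 25 (64%) has lower limit 0.425, while 13 of 21 (62%) has 0.384. The rates almost agree, yet one interval excludes 40% and the other does not, simply because four subjects were removed. The pooled line itself, 15 of 25, has lower limit 0.387. A comparison of that kind would respond to lost sample size as much as to any TKI effect.

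**The case against.** The strongest case on the other side has four parts.

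- **Entry status.** Every subject must be flow-MRD positive at entry (Section 4.2.1). The exemption in Section 4.2.8 is worded around a washout, so it naturally covers patients already on a TKI. In them MRD has persisted despite the TKI, and clearance after adding blinatumomab points less to the TKI. This stands as mitigation. It does not settle the matter, because nothing prevents a TKI being started alongside blinatumomab.
- **Evidence of TKI activity.** Section 1.2 speaks only of Ph+ ALL. It says nothing about Ph-like disease, the subgroup that Section 4.2.1 actually names, or about clearing MRD in patients in remission. A reader might infer that the protocol regards TKIs as equally active in all users; it does not say so.
- **Size.** A reader might infer that TKI responses are likely to carry the trial to a false success, citing 0.17. That figure needs four users, all responding, and the 15-response line. At 40% response there is no inflation. At 17 of 25, the same worst case gives 0.035, close to the stated error rate of 0.0333. The documents do not support the stronger reading.
- **Purpose.** This is a small Phase 2 study whose primary endpoint is reported as an estimate with a CI, and a split by TKI use could be tabulated later from recorded data. That is true, but a split chosen after the results are known carries less weight, and specifying it now costs almost nothing.

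**Conclusion.** The point holds as one of attribution. The plan allows a second active treatment in an identifiable subgroup, pools that subgroup into the primary analysis, and states its objective as the efficacy of blinatumomab. A pooled rate above 40% would therefore describe blinatumomab with or without a TKI.

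The numerical consequence is conditional. For 2 to 4 users responding at 60–100%, with the others at 40%, the expected rate shifts upward by 1.6 to 9.6 percentage points. The chance of reaching 15 of 25 is 0.048 to 0.174, against 0.034 with no TKI effect. The chance of reaching 17 of 25 is at most 0.035, against 0.004. These ranges rest on two quantities that the documents do not supply, and Section 10.4's two success lines (60% and 67%) give very different answers. MRD positivity at entry lessens the concern for subjects already on a TKI. The gap is worth closing before analysis, but it does not invalidate the design.

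**What to change.** Leave the eligibility text as it is and add to Section 10.7.2:

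1. A pre-specified sensitivity analysis: the FC-MRD-negative proportion with exact 95% CI, excluding subjects who took a concomitant TKI. Define this from the medication record, for example any TKI use between the first day of blinatumomab and the marrow that determines response.
2. A listing of response by TKI use, showing whether the TKI was recorded at baseline or only later.
3. A reporting rule: if the non-TKI point estimate is materially lower than the pooled one, the conclusion is worded as applying to blinatumomab with or without a TKI. The team should state beforehand what counts as material; the documents offer no margin. The rule should not depend on whether each interval excludes 40%, for the reason in Step 4 of the working.

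The data are already collected, so the cost is one table line and a short listing. The downside is a wider interval in the subset. The comparison is also descriptive: a lower rate without TKI users could reflect disease biology as well as the TKI.

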6.3.2 Pregnancy and Lactation

Pregnancy Category Unknown: The effect of blinatumomab on fertility has not been evaluated. Blinatumomab is not recommended in pregnant women and in women of childbearing potential not using contraception. It is not known whether blinatumomab or its metabolites are excreted in human milk. Women are not allowed to breastfeed while receiving blinatumomab.

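### Criterion 4.2.12 counts post-treatment contraception from the last chemotherapy dose, not from blinatumomab, so cover after the study drug can fall to zero

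*Combined protocol and SAP*

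**What the plan says.** Criterion 4.2.12 asks sexually active women of child-bearing potential to use contraception "for the duration of treatment and for 2 months after the last dose of chemotherapy". The sentence for men has the same end point: "Sexually active men must agree to use barrier contraceptive for the duration of treatment and for 2 months after the last dose of chemotherapy". Neither sentence mentions the last dose of blinatumomab.

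Other sections bear on what the word chemotherapy can refer to:

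- The Protocol Summary names blinatumomab as the study agent. Section 5.5.1 limits treatment to blinatumomab cycles, and the plan in 6.1 schedules no chemotherapy.
- Criterion 4.2.6 sets a washout: "At least 7 days must have elapsed from prior chemotherapy".
- Criterion 4.3.2 excludes patients "Receiving concomitant chemotherapy (with the exception of a tyrosine kinase inhibitor" for Philadelphia-positive or Philadelphia-like disease, and leaves room for therapy that the protocol itself specifies. Criterion 4.2.8 permits the same TKIs on study.
- Section 1.2, in its discussion of neurological events, states that intrathecal chemotherapy is given before blinatumomab starts on this study.
- On fetal risk, 4.3.4 says "The agents used in this study are known to be teratogenic to a fetus". Section 6.3.2 gives the pregnancy category as unknown and adds "Blinatumomab is not recommended in pregnant women and in women of childbearing potential not using contraception". It gives no period after the last dose.

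**The concern.** A contraception rule for a study drug would be expected to run from the last dose of that drug. Here the part that extends beyond treatment is tied to a different class of agent. The protocol does not use chemotherapy as a general word for study treatment. The Protocol Summary lists chemotherapy, immunotherapy and radiotherapy as separate prior therapies. Chemotherapy has its own washout in 4.2.6, apart from those for biologics, monoclonal antibodies and immunotherapy in 4.2.8 to 4.2.10. Section 1.2 describes blinatumomab as a bispecific antibody.

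Taken literally, the clock can start before the first infusion and run out before the last one. What is at stake is a reproductive-safety condition that subjects accept at entry, in a trial open to patients up to age 25. With two sites and an undefined anchor, the same criterion could be applied in different ways.

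**Working it through.** The plan states no figure to reproduce, and no sample size or error rate is involved. The check is day arithmetic, with Day 1 as the first day of blinatumomab and Day 0 as the day before it.

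**When the drug ends (from 6.1)**

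- One cycle: Day 28.
- Two full cycles: 28 + 14 + 28 = Day 70.
- Second cycle shortened to 14 days while a donor is awaited, the example in 6.1: 28 + 14 + 14 = Day 56.

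Treatment is taken to end with the infusion, because the 14 days that follow each cycle in the 6.1 table are labelled as free of treatment.

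**Assumptions**

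- Two months is 60 or 61 days.
- The last chemotherapy falls between Day −6, which is 7 days before Day 1 (the 4.2.6 minimum), and Day 1 itself, which allows for an intrathecal dose just before the infusion as Section 1.2 suggests.

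**Formula**

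End of period = day of last chemotherapy + 60 or 61. Days of required cover after the drug = max(0, end of period − day the drug ends).

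Earliest end: −6 + 60 = Day 54. Latest end: 1 + 61 = Day 62.

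| Course | Drug ends | Earliest case | Latest case | Cover after drug |
|---|---|---|---|---|
| Two full cycles | Day 70 | 54 − 70 < 0 | 62 − 70 < 0 | 0 days |
| Shortened second cycle | Day 56 | 54 − 56 < 0 | 62 − 56 = 6 | 0–6 days |
| One cycle | Day 28 | 54 − 28 = 26 | 62 − 28 = 34 | 26–34 days |

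**Other readings**

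- *Chemotherapy ended earlier.* Every figure shrinks. After one cycle, cover reaches zero once the last chemotherapy is on or before Day 28 − 60 = −32 (or 28 − 61 = −33), which is 33 to 34 days before Day 1.
- *No chemotherapy counts.* Only the requirement during treatment remains, so cover after the drug is 0 days for every course.
- *A TKI or transplant conditioning counts.* The period runs later for those subjects. The documents do not give dates from which to size this.

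**Does the intrathecal statement settle the anchor?** No. Section 1.2 says that intrathecal chemotherapy comes before blinatumomab, but 6.1 schedules none, and the lumbar punctures in 5.1.3 and 5.3.1 are listed only for CSF cytology and cell count. A dose as late as Day 1 still gives Day 62 at the latest, 8 days before two full cycles finish (70 − 62 = 8).

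**The case against.** The strongest reply is that the sentence is cumulative. Contraception is required throughout treatment on every reading, and a reader who has just met the word treatment may take the last dose to be the last dose of that treatment. Every subject must also intend to go directly to transplant (4.2.2). If conditioning counts as chemotherapy, the period runs well past blinatumomab for those who are transplanted. The first part stands as a description of how some readers would apply the rule. It does not remove the defect, because the same sentence uses treatment and chemotherapy as two anchors and the rest of the protocol keeps chemotherapy distinct from antibodies and immunotherapy. The second part depends on an unstated reading and does not help subjects who come off study still MRD positive after Cycle 2.

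Three stronger readings are tempting, and the documents do not support them:

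- A reader might infer that the study gives no chemotherapy and forbids it outright. Section 1.2 says that intrathecal chemotherapy is given beforehand, and 4.3.2 carries both a TKI exception and an allowance for protocol-specified therapy. The texts conflict, and neither side can be taken as settled.
- A reader might infer that anyone who stops early has no requirement afterwards. Under the assumptions used here, a subject who stops on Day 14 keeps 54 − 14 = 40 to 62 − 14 = 48 days. Zero arises with late completion, with chemotherapy that ended well before Day 1, or if no chemotherapy counts.
- A reader might treat the teratogenicity statements as a second defect of equal weight. Sections 4.3.4 and 6.3.2 are in tension, but both point towards avoiding pregnancy on study, and neither bears on when the period ends.

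The consent form was not available for review, so it may already use a different anchor.

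**Conclusion.** The point holds as a wrongly anchored and inconsistently defined safety rule. It is not proof that no contraception is required after the drug. Criterion 4.2.12 never counts from blinatumomab, and no other section supplies a period after the last dose. If the word means chemotherapy given before the infusion, required cover after the drug ranges from none (two full cycles) to about 26–34 days (one cycle). This rests on a 60–61 day reading of 2 months and a last chemotherapy between 7 days before Day 1 and Day 1. The result for two full cycles does not change anywhere in that range, while the one-cycle result falls if chemotherapy ended earlier. How many subjects would be affected cannot be sized from the documents. No endpoint, sample size, error rate or analysis depends on this.

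**What to change.** Reconcile 4.2.12 with 4.3.2, 4.3.4, 6.1, 6.3.2 and the intrathecal statement in Section 1.2, so that the criterion names the study agent whose last dose starts the period, for both sexes. In the same edit, state whether intrathecal chemotherapy is part of this study, say whether a permitted TKI or transplant conditioning affects the period, and align the two statements on fetal risk. The sponsor's clinical lead sets the interval; this review proposes none. Check the consent form and change it only if its wording does not match. The cost is a short wording amendment, mainly to one eligibility criterion with consequential edits to the sections named, plus a consent form revision if one is needed. No new data collection or analysis is involved.
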